9.2 Inclusion Criteria

1. For females and males 18 years old or older: females should be on adequate contraception if they are of child-bearing potential, which should be documented by a clinician, unless patients or their spouse/partner(s) have previously undergone a sterilization procedure. Adequate contraception will be considered:
 - Intrauterine device (IUD),
 - Hormone implants,
 - Injectable contraceptives,
 - Oral contraceptives plus a barrier method (male condom, female condom or diaphragm),
 - Abstinence, or
 - A vasectomized partner.
2. Meet revised ACR criteria and 2012 SLICC criteria for SLE and have: a) a baseline SLEDAI-2K ≥ 4 and <20 or a clinical SLEDAI-2K ≥ 2 (not considering anti-dsDNA or complement levels) and b) lack of BILAG A flare at baseline (See Appendix 3).
3. Stable doses of immunosuppressants and/or antimalarials for at least 3 months, and/or corticosteroids for at least 2 weeks. The prednisone dose may be increased after screening visit as long as the total dose is less than 20 mg of prednisone or equivalent per day and the subject is on stable dose for at least 2 weeks prior to their Day 1 visit. If on statins, should have been on stable doses for at least 6 months.
4. Allowed concomitant lupus-related medications
Antimalarials,
Prednisone ≤ 20 mg daily or equivalent doses of other corticosteroids;
Immunosuppressants:

Mycophenolate mofetil, up to 3000 mg/day,

Methotrexate, up to 30 mg/week,

Azathioprine, up to 3 mg/kg/day,

Leflunomide, up to 20 mg/day,

Cyclosporine, up to 5 mg/kg/day

Tacrolimus, up to 0.1 mg/kg/day

NSAIDs and aspirin

Note: While it would be highly desirable to maintain corticosteroid dosage at constant level for trial duration, it is impractical to anticipate that all patients with active SLE can be maintained without therapy modification for an 8-month period. Because corticosteroids are acceptable agents for treatment of the vast majority of minor lupus flares, and patients with major flares (BILAG 2004 A or recent change in medications) will be excluded, this will provide standardized treatment across study population that can be easily analyzed. An increase in prednisone dose of less than or equal to 10 mg/day from their prednisone dose at study entry will be permitted during the trial for increased disease activity with a standardized taper allowable in small monthly decrements to the patient's baseline dose or 5 mg/day, whichever is less.

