10 MONITORING SUBJECTS AND CRITERIA FOR WITHDRAWAL

10.1 Patient Withdrawal and Termination Criteria.

Subjects will be informed that they may withdraw or be excluded from the study at any time. Our intention is to maintain stable doses of immunosuppression and antimalarials for the

duration of the trial. On occasion, doses are adjusted to treat SLE activity. While not ideal, we anticipate that over the duration of 8 months, outside providers may want to adjust or add new immunosuppressive therapy. In the event of these changes, each of these instances will be reviewed by the Principal Investigator to determine continuation or withdrawal from the trial to maintain scientific integrity.

The following conditions will require the discontinuation of study agent:

1. Subjects may voluntarily withdraw at any point
2. Flares not responding to the treatment above or if, in the opinion of the responsible investigator, the subject needs immediate immunosuppressive therapy that is not allowed in the protocol
3. Any Grade 4 adverse event that is unexpected and at least possibly, probably or definitely related to study drug
4. More than 1 “no-show” for a visit
5. Becoming pregnant after baseline visit. The subject will be followed for the outcome of the pregnancy.
6. Any other reason that, in the opinion of the responsible investigator, poses unacceptable risk to the subject.
7. Nevertheless, LFTs will be monitored on all patients at each study visit and those patients with LFTs >2x upper limit at Screening visit will be excluded. If during the trial, LFTs increase to > than 3x fold the upper limit of normal (ULN), levels will be rechecked within 36 hours and if elevation >3 ULN persists and there are not alternative etiologies, therapy will be discontinued. If LFTs are elevated >2 but < 3x ULN (after confirming within 48 hours), we will investigate etiology of liver enzyme elevation and cautiously reinstate therapy if alternative etiology is found. For patients with NAFLD that are enrolled, based on recent clinical trials that have been published (Cusi K et al. Annals of Internal Medicine 2016) assessing the role of long-term pioglitazone treatment for nonalcoholic steatohepatitis, we will include only patients that have LFTs < 3 times ULN. If there is an increase to >3 times ULN once study drug starts during monitoring (confirmed within 24 hours), drug will be stopped.

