covariates other than treatment and period effects. There are several confounding variables, especially medications that could contribute towards the variation in the outcome. We will expand the regression models by including them as predictors. If the number of confounding variables is large, we will use investigate a propensity score matching analysis. For Specific Aim 2, we will define a dichotomous clinical endpoint measuring lupus disease activity. Patients achieving an improvement of the SLEDAI-2K by 20%, a significant improvement in PGA and the absence of a BILAG 2004 A or B flare will be considered to have improved. Others will be defined as not having improved. The analysis for this score will be similar to the one proposed for Specific Aim 1. A GEE model will be used to assess treatment differences. We will also investigate the separate effects of each of these measures. The same approach used in Aim 1 will be taken for confounding variables using regression or propensity score adjustment. We will begin the investigation of Aim 3, assessment of innate and adaptive immune abnormalities in SLE, with a graphical analysis of the variables. We use multivariate methods to determine good summary measures of the various factors and compare the two treatments using the same models as defined for Aims 1 and 2.

Our primary analysis will be performed as an intent-to-treat analysis. If the subjects providing complete data are systematically different from those who dropped out, then the estimates based only on completers will be biased. We will investigate adjusting for differences in the populations who are completers and noncompleters and will consider multiple imputation to impute the missing values. Before the database is locked and final analysis performed, violations will be assessed on a case-by-case basis by the PI to determine if the medication change was such that it would adversely affect the study results. If changes may adversely affect data interpretation, subjects will be dropped from final analysis. A post hoc analysis of disease activity, measured by SLEDAI-2K, will be adjusted for burst steroids in excess of that permitted by the protocol. Analysis of prednisone doses, daily and cumulative will also be included.

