11.1 Power and Sample Size

We arrived at sample size based on previous publications for arterial stiffness and vascular dysfunction observed in SLE^{92, 101-103} as well as on our recently completed RA trial. To achieve this sample size, we will be recruiting 100 patients, assuming a 20% or more dropout rate (see below). The actual analysis will be more powerful and will use data on all subjects including those who provide partial information. Based on our previous experience with the CV lupus cohort and on published literature on cross-over designs using pioglitazone to measure CV markers in other populations, we estimate our dropout rate to be between 3-20%. We have then projected a 20% drop-out rate that includes both drop-outs, as well as the few people who are deemed protocol violators because of significant changes in immunosuppressive or vascular medications. This sample will give us power to detect moderate standardized differences for the other variables measured in this study. As this is a “proof of concept” study, we estimate it is

important to detect at least moderate differences in outcome for them to be clinically meaningful.

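### The primary analysis is called intent-to-treat, but the same paragraph drops subjects from the final analysis for post-randomisation medication changes

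*Combined protocol and SAP*

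**What the plan says.** Section 11 (Data Analysis) states: "Our primary analysis will be performed as an intent-to-treat analysis". It warns that estimates from completers alone can be biased and contemplates multiple imputation. Still in that paragraph, it says that before lock "violations will be assessed on a case-by-case basis by the PI", and then: "If changes may adversely affect data interpretation, subjects will be dropped from final analysis". It adds a post hoc SLEDAI-2K analysis that "will be adjusted for burst steroids in excess of that permitted by the protocol".

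Other sections bear on who is analysed:

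- Section 10.2 keeps patients who complete only one arm in the analysis, although they are also replaced.
- Section 11.1 says the actual analysis "will use data on all subjects including those who provide partial information". It also counts within the projected 20% loss "the few people who are deemed protocol violators because of significant changes in immunosuppressive or vascular medications".
- Section 10.1 says of background therapy: "On occasion, doses are adjusted to treat SLE activity". It has the PI review added or adjusted immunosuppression during the trial to decide between continuation and withdrawal.
- Section 10.4 keeps investigators blinded for the whole study period.

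**The concern.** Removing randomised patients because of something that happened after randomisation is not intent-to-treat. The plan gives the label and the contrary instruction in one paragraph, and does not name a separate per-protocol set to which the instruction could belong. Two analysts following Section 11 faithfully could therefore analyse different patients for the primary vascular endpoints.

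The removal is also not plainly unrelated to treatment. Section 10.1 ties medication changes to lupus activity, and Hypothesis 3 in Section 7 is that pioglitazone lowers that activity. If the hypothesis is right, qualifying changes would tend to be more frequent in placebo periods, and patients would be lost for a reason that depends on treatment, however well the blind is kept.

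The criterion is loose as well. Section 11 gives a purpose (possible harm to interpretation) and Section 11.1 a category (significant changes in immunosuppressive or vascular medication), but neither gives a threshold.

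**Working it through.** **Text.** The sections fall on two sides.

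- Keep everyone: the intent-to-treat sentence and the imputation plan (Section 11), one-arm patients retained (Section 10.2), data on all subjects used (Section 11.1).
- Remove some: the drop sentence (Section 11). In Section 11 the phrase final analysis also names what is performed after database lock, so it does not naturally denote a side analysis.
- Compatible with either: the 20% loss that includes violators (Section 11.1). It may be only a conservative sizing margin, but it does not rule out exclusion.

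**Size.** The plan has no figure to reproduce here: it states no alpha, power, SD, effect size or violation rate. The inputs below are assumptions, except the 75 patients, which is the upper completion target in Section 8.

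1. Two-sided alpha 0.05, paired comparison, n = 75. The standardised paired difference that gives 80% power is 0.328.
2. Let violations occur in a fraction p0 of placebo periods and p1 of pioglitazone periods, independently of each other and of outcome. The fraction of patients dropped is 1 − (1 − p0)(1 − p1).
3. Closest to the plan's description of violators as few, p0 = 2% and p1 = 1%: 1 − 0.98 × 0.99 = 0.0298. Then 75 × 0.9702 = 72.8, about 73 patients, and power at the same effect is 78.9%.
4. Range: with 5% and 2.5%, 1 − 0.95 × 0.975 = 0.074, leaving about 69 patients and power of about 77%. With 10% and 5%, 1 − 0.90 × 0.95 = 0.145, leaving about 64 patients and power of about 73%. The last case fits the word few poorly.

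**Selection linked to outcome.** Suppose a violation occurs when standardised disease activity in a period passes a threshold, with between-period correlation 0.6 and a drug effect of 0.2 to 0.5 SD on activity. With 2% of placebo periods in violation, dropping violators shrinks the activity effect by about 3% to 4%. A vascular outcome correlated 0.1 to 0.5 with activity shifts by about 0.001 to 0.007 SD. With 10%, the activity effect shrinks by about 10% to 12% and the vascular shift is at most about 0.025 SD. The shift towards no effect follows from this model and cannot be derived from the documents.

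**The case against.** The best defence has four parts.

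- **Timing and blinding.** The PI decides before lock and is blinded. This stands: it prevents knowing removal by arm and settles who is dropped before results exist. It does not stop the exclusions from depending on treatment through disease activity. A reader might infer that the analysis set could be chosen once results are known, with inflated type I error. The documents do not support that, since no passage permits reporting whichever set is significant.
- **The sizing allowance.** A reader might take the violators in Section 11.1 as proof that they will be excluded. Planning conservatively for losses and then analysing everyone is coherent, so that paragraph is ambiguous and is not a second contradiction.
- **Steroid bursts.** A reader might see another conflict in the planned adjustment for excess bursts, which needs those patients kept. That analysis is labelled post hoc and concerns disease activity, a secondary endpoint, so it says little about the primary one. It does show that the exclusion criteria need detail. Section 9.2 names steroids apart from immunosuppressants ("Stable doses of immunosuppressants and/or antimalarials for at least 3 months, and/or corticosteroids for at least 2 weeks"), so the category in Section 11.1 does not settle whether an excess burst counts.
- **Small effect.** With few violators the numbers barely move. This also stands. Because Section 11.1 already places violators inside the 20% loss, subtracting them from 75 completers may count them twice. The GEE planned in Section 11 can also use partial data, which the paired calculation ignores.

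**Conclusion.** The concern holds as a contradiction in the text. Section 11 labels the primary analysis intent-to-treat and then instructs a post-randomisation exclusion that nothing confines to a secondary analysis. It would go too far to say that the plan leaves the analysis population wholly open, because several passages point to keeping everyone and one sentence contradicts them.

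The likely quantitative consequence is modest: about 3% of patients and about one percentage point of power under the 2% and 1% assumption. Any bias is likely small if violators are few. Both statements rest on assumed rates and a simplified paired analysis. The point should be fixed because following the rule as written breaks intent-to-treat and the repair is cheap.

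**What to change.** 1. In Section 11, remove the drop rule from the primary analysis. Analyse all randomised patients by assigned sequence, whatever their medication changes, using the planned GEE with partial data. For patients without later data, including those withdrawn after the PI's review under Section 10.1, use the multiple imputation that Section 11 already contemplates. Deleting the drop sentence alone would not recover those data.
2. Confine the PI's medication-change exclusions to a per-protocol sensitivity analysis. List the qualifying changes before unblinding, and say whether steroid bursts above the permitted amount count.
3. In Section 11.1, state that violators in the 20% allowance are a planning margin and are not excluded from the primary analysis.

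The cost is wording in Sections 11 and 11.1 and one additional sensitivity table. The primary estimate will then include the effect of medication changes and some added noise from them.

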11.1 Power and Sample Size

We arrived at sample size based on previous publications for arterial stiffness and vascular dysfunction observed in SLE^{92, 101-103} as well as on our recently completed RA trial. To achieve this sample size, we will be recruiting 100 patients, assuming a 20% or more dropout rate (see below). The actual analysis will be more powerful and will use data on all subjects including those who provide partial information. Based on our previous experience with the CV lupus cohort and on published literature on cross-over designs using pioglitazone to measure CV markers in other populations, we estimate our dropout rate to be between 3-20%. We have then projected a 20% drop-out rate that includes both drop-outs, as well as the few people who are deemed protocol violators because of significant changes in immunosuppressive or vascular medications. This sample will give us power to detect moderate standardized differences for the other variables measured in this study. As this is a “proof of concept” study, we estimate it is

important to detect at least moderate differences in outcome for them to be clinically meaningful.

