7 OBJECTIVES

The major goal of the proposed research is to assess the effect of a targeted pharmacotherapeutic intervention – the administration of the PPAR- γ agonist pioglitazone – in SLE on:

- vascular endothelial function (primary endpoint), a predictor of CV risk
- SLE disease activity (secondary endpoint).

This randomized clinical trial, with a modest sample size, can both serve as a “proof of concept” study for the potential utility of TZDs in SLE, and inform us on which surrogate outcomes or biomarkers may be useful in future lupus studies aimed at CV/immunomodulatory outcomes.

Aim 1: To conduct a randomized, double-blind, placebo controlled, crossover, proof-of-concept clinical trial in adult SLE patients comparing the effects of pioglitazone vs. placebo on vascular endothelial function and blood vessel inflammation. Primary outcome measures will be large

vessel arterial stiffness, measured either by cardio-ankle vascular index (CAVI) or pulse wave velocity (PWV, assessed by Sphygmocor) (both tests to assess large vessel arterial stiffness), and assessment of microvascular peripheral arterial tone (PAT). Secondary outcome measures of atherosclerosis risk and metabolic disturbances will include proinflammatory HDL (piHDL) levels and HDL cargo, lipoprotein function, lipid profile and insulin resistance and EPC phenotype and function. In addition, modulation of arterial inflammation will be assessed in a subset of patients by neck to groin fluorodeoxyglucose positron emission tomography CT (FDG PET/CT).

Hypothesis 1: Endothelial function and arterial compliance will significantly improve in SLE patients treated with pioglitazone when compared to placebo, while arterial inflammation will decrease.

Hypothesis 2: Pioglitazone will alter HDL cargo function, decrease proinflammatory HDL levels and insulin resistance, and improve markers of vascular repair in SLE.

Aim 2: To assess the ability of pioglitazone to reduce SLE disease activity, when added to standard lupus care, as assessed by the SLEDAI-2K disease activity index (SLEDAI-2K), lack of A or B flares on the British Isles Lupus Activity Group (BILAG 2004) score, and physician's global assessment (PGA) (See Appendix sections 2,3,7). Serological markers of SLE activity and various cytokines considered important in lupus pathogenesis will also be quantified.

Hypothesis 3: SLE Disease activity will decrease in SLE patients when treated with pioglitazone vs. placebo.

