SphygmoCor Pulse Wave Velocity System- a tool that derives a pressure pulse waveform using the pressure tonometer and an ECG signal simultaneously. Arterial tonometry uses a pressure sensor to detect the speed of a pulse wave and may indicate a problem in the arteries.

SphygmoCor Pulse Wave Monitoring System– a tool that provides an estimated pressure waveform from the ascending aorta.

PAT: The Endopat2000 device measures finger microvascular endothelial function in a fully-automated fashion before and after reactive hyperemia (RH-PAT). RH-PAT response is independently predicted by traditional and novel CV risk factors¹¹⁴. PAT test is operator-independent, with higher inter-day reproducibility than US conduit studies¹¹⁵. PAT dysfunction occurs in SLE in association with IFN signatures¹¹⁶. While pioglitazone did not modulate PAT in RA patients⁵, it will be important to establish the role of this drug in microvascular function in SLE. Finger PAT signal is recorded by non-invasive, modified plethysmography-based probes, then to digital media. PAT software calculates various outcomes, the main one being the RH-PAT index=ratio of average RH-PAT PWA in a finger of the occluded arm for a 60 second period beginning 1 minute after blood pressure cuff-release, compared to average PWA during the 210 second-long baseline pre-occluded period. The ratio is normalized to the PAT index in the control arm.

To simplify, we will refer to the CAVI, PWV and EndoPAT tests as “vascular function studies”.

Assessment of vascular inflammation using [18F]-2-fluoro-2-deoxy-D-glucose (FDG) imaging using positron-emission tomography (PET)/computed tomography (CT)): FDG-PET/CT enables highly precise, novel measurements of inflammatory activity including vascular, visceral, and whole body inflammation in vivo. The range of applications for FDG-PET imaging has been expanded to include the evaluation of activity of atherosclerotic plaque. Importantly, in diabetics or patients with glucose intolerance, pioglitazone attenuated left main trunk inflammation in a glucose-lowering independent manner when examined after 4 months of treatments [9 References](#)⁴. This will be performed in a subset of 30 patients given the logistics of scheduling imaging studies at the Clinical Center.

b) Metabolic parameters and vasculogenesis profile

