Insulin resistance: This is an important CV risk factor¹¹⁷⁻¹¹⁹ and a significant proportion of SLE patients exhibit this abnormality^{120,121}. Homeostatic measurements like the HOMA calculation allow for an easy assessment of insulin resistance^{122,123}. In lupus-prone mice, pioglitazone induced significant changes in insulin resistance. Furthermore, in the RA trial, 3 months of pioglitazone changes led to substantial improvements in this parameter, as assessed by HOMA2 calculations⁵.

piHDL and lipids: Patients with active SLE exhibit a proatherogenic lipid profile with low HDL, high triglycerides and dysfunctional HDL¹²⁴. Pioglitazone improves lipid profiles [125,126](#) in DM, in non-diabetics and in murine SLE⁸⁶. We will monitor lipid profile, oxidized HDL and cholesterol efflux activity of HDL from all subjects ex vivo before and after therapy. HDL oxidation and proteome profiles will be determined by MS in a subset of patients in the trial, NMR to assess lipoprotein particles will also be performed. These

studies will identify whether pioglitazone treatment improves HDL oxidation, remodels HDL proteome and renders the lipoprotein more functional.

EPC numbers and function: As SLE EPCs are decreased in number and display decreased function, and pioglitazone has been shown to have positive effects on vasculogenesis, we will quantify EPC numbers and function as previously described by our group, at various time-points³⁵.

8.1.2 ***Specific Aim 2: Effect of pioglitazone on SLE disease activity***

In clinical trials, the main methods to assess SLE activity are the SLEDAI-2K and the BILAG 2004. The investigators on this study have significant expertise in the use of these tools and have participated in clinical trials that used both methods to score disease activity.

a) –SLEDAI 2K: This validated scoring system is a modification of the original SLEDAI-2K system to reflect persistent, active disease in those descriptors that had previously only considered new or recurrent occurrences⁵, The score can be between 0-10⁵. It is based on the presence of 24 descriptors in nine organ systems over the preceding 30 days. Descriptors are documented as present or absent. Each descriptor has a weighted score. Higher scores represent higher disease activity.(see Appendix).

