9.5 Study Visits

9.5.1 *Baseline visit and 5-month +/- 7 days (post-washout) visit*

- a. Baseline visit will include medical history. The baseline and 5-month (post-washout) visits will consist of a physical exam, and blood draw for biomarkers (Table 3). SF-36, PGA, disease activity (BILAG 2004, SLEDAI-2K) and vascular measurements will be determined and subjects will be issued a 3-month supply of blinded study drug or placebo with instructions. The first week of each treatment arm, patients will take two 15 mg capsules of pioglitazone daily (30 mg total daily dose) and, if no significant side effects develop (primarily fluid retention), will increase to three 15 mg capsules (45 mg total daily dose). Subjects will be instructed to follow the same titration for the placebo arm. Patients will be called prior to increasing the dose to 45 mg to question patients about rapid weight gain (>5 pounds in a week), significant edema or other side effects. Patients will be called 1-2 weeks after increasing dose to 45 mg daily to assess tolerability. If 45 mg dose is not well tolerated but the 30 mg dose is well tolerated, dose will be decreased back to 30 mg daily for duration of trial. PET/CT exams will be performed in 15 patients initially randomized to placebo and 15 patients initially randomized to pioglitazone and the investigators will be blinded to this. PET/CT studies will only be performed at baseline and month 3. Subjects can opt out of the PET/CT scan and still participate in the study. Patients will be asked to participate at baseline until we reach 15 patients/group. If a patient is found to have an acute infection at the baseline visit, they will be given antibiotics and their next visit will be scheduled for no more than 4 weeks later, at which time they will start the study medication. We will repeat only baseline clinical labs at this extra visit; we will not repeat PET/CT, vascular function studies or research sample collection. If a patient has an abnormal lab result at the baseline visit that requires a repeat, the patients next visit will be scheduled no more than 4 weeks later, at which time if the abnormal lab has improved or normalized they will

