start the study medication. We will not repeat PET/CT, vascular function studies or research sample collection. If any subjects are enrolled in our Natural History of SLE Protocol (94-AR-0066) and have undergone a research-indicated PET/CT scan as part of that study within the 6 months prior to their baseline visit, we will use that data for their baseline values and will only perform the PET/CT scan at the month 3 visit.

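### The section 11.1 power statement does not except FDG-PET/CT, a first-period comparison of 15 v 15 that lacks power for a moderate difference unless the baseline correlation is about 0.88 or more

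*Combined protocol and SAP*

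**What the plan says.** Section 11.1 gives no numerical power. After describing recruitment of 100 patients and a projected 20% dropout, it says "This sample will give us power to detect moderate standardized differences for the other variables measured in this study", and adds that it is "important to detect at least moderate differences in outcome for them to be clinically meaningful". It does not define a moderate difference and states no significance level, target power or SD.

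FDG-PET/CT is one of the variables measured. Hypothesis 1 in section 7 predicts better endothelial function and arterial compliance "when compared to placebo, while arterial inflammation will decrease". Section 11 names FDG-PET/CT beside CAVI/Sphygmocor and PAT as an Aim 1 outcome to be analysed separately.

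Its sample and schedule differ from the rest of the trial:

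- Section 8.1.1: "This will be performed in a subset of 30 patients given the logistics of scheduling imaging studies at the Clinical Center".
- Section 9.5.1: "PET/CT exams will be performed in 15 patients initially randomized to placebo and 15 patients initially randomized to pioglitazone", and "PET/CT studies will only be performed at baseline and month 3". Section 9.5.3 and Table 3 agree.
- Section 9.5.1 also lets some patients supply a research scan from the natural history protocol as their baseline: if it was done "within the 6 months prior to their baseline visit, we will use that data for their baseline values".

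Section 11 describes outcomes measured on four occasions per patient. It plans matched-pair differences compared between sequences, a carryover assessment, a period effect and two baselines. It then specifies a GEE with treatment and baseline indicators, unstructured covariance and robust standard errors. No separate model or power statement for PET appears.

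**The concern.** No patient is scanned in the second period, so no patient contributes a pioglitazone-minus-placebo PET difference. The efficiency that a crossover gains from within-patient comparison is not available, and the number of patients is less than half that of the main trial. The power sentence nevertheless covers PET as written.

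Section 11.1 itself treats a moderate difference as the least that is clinically meaningful. A reader who relies on that sentence could take a null PET result as evidence against a moderate effect on arterial inflammation, when the design could easily have missed one. Section 11 does not commit to an interval that would show this. An analyst following section 11 literally would also meet terms that these scans cannot estimate.

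**Working it through.** **Inputs from the plan.** 15 patients per initial assignment; scans at baseline and month 3 only (sections 9.5.1, 9.5.3, Table 3). Main crossover: up to 75 completers (section 8); section 12.2.2.4 refers to 70 patients.

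**Assumptions, not in the plan.** Two-sided 5% test; moderate = 0.5 between-patient SD; baseline to month-3 correlation r, varied. There is no stated power figure to reproduce.

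**1. Unadjusted month-3 comparison.** Noncentrality = 0.5 × √(15/2) = 1.37 on 28 df, critical t = 2.048. Power is 26%. The difference detectable with 80% power is 1.06 SD. The expected 95% half-width is 2.048 × √(2/15) = 0.75 SD.

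**2. Baseline-adjusted comparison.** The residual SD is √(1 − r²), so the noncentrality is 0.5/√(1 − r²) × √(15/2) on 27 df, critical t = 2.052. The half-width is 2.052 × √(2/15) × √(1 − r²).

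| r | √(1 − r²) | Noncentrality | Power at 0.5 SD | Detectable at 80% | 95% half-width |
|---|---|---|---|---|---|
| 0.5 | 0.866 | 1.58 | 33% | 0.92 SD | 0.65 SD |
| 0.7 | 0.714 | 1.92 | 46% | 0.76 SD | 0.54 SD |
| 0.8 | 0.600 | 2.28 | 60% | 0.64 SD | 0.45 SD |
| 0.9 | 0.436 | 3.14 | 86% | 0.46 SD | 0.33 SD |

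Power reaches 80% at r = 0.882. The half-width falls to 0.5 SD only at r = 0.745; below that, an observed difference of zero still leaves 0.5 SD inside the expected interval. These formulas ignore chance baseline imbalance. Averaging over it lowers the four powers slightly, to 32%, 44%, 58% and 84%.

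**3. Sensitivity of the required r.** It is 0.926 for 0.4 SD, 0.825 for 0.6 SD, 0.752 for 0.7 SD and 0.657 for 0.8 SD. For 0.5 SD it is 0.844 with a one-sided 5% test, 0.889 with a change-score analysis, and 0.909 if only 12 v 12 are evaluable.

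**4. Main crossover on the same scale.** The paired effect is 0.5/√(2(1 − r)), where r is now the within-patient correlation between periods. With 75 pairs, power is 86% at r = 0 and 99% at r = 0.5. With 70 it is 83% and 98%. With 56 (70 × 0.8, a pessimistic case) it is 74% and 96%. The section 11.1 statement is therefore plausible for variables measured in both periods in the full sample.

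**5. What the section 11 model can estimate from PET data.** The PET design has four kinds of record: baseline and month 3 in each initial assignment. With intercept, treatment and baseline terms the design matrix has rank 3 of 3, so the GEE can be fitted, but its treatment coefficient is a between-patient, first-period contrast. Adding a period term leaves rank 3 of 4, against 4 of 4 when all four visits are present. Matched-pair differences, carryover and a second baseline need second-period scans and do not exist for PET.

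**6. The GEE as written.** It was simulated with 15 v 15 bivariate normal data, unstructured covariance, uncorrected robust standard errors and critical value 1.96, using 10,000 runs per setting. Power was 40%, 53%, 66% and 89% at r = 0.5, 0.7, 0.8 and 0.9. Type I error, however, was 7.4% to 8.4% instead of 5%. Held to a true 5%, power was 32%, 42%, 60% and 84%, so the choice of model does not rescue the claim.

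**The case against.** The strongest reply is that the sample in the power sentence is the full crossover sample just described, and that the PET subset is disclosed openly elsewhere with its size, reason and schedule. On that reading section 11.1 omits an exception but makes no false claim. Yet the sentence extends to every other variable measured in the study, and nothing else in the plan covers PET power.

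A second reply is that the four-occasion sentence concerns primary and secondary outcomes, while section 7 introduces PET after both lists. That ambiguity is real. Section 11 still places PET among the Aim 1 outcomes and gives it no model of its own.

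Third, a sensible analyst would drop the inestimable terms, and the treatment-plus-baseline GEE can be fitted. That is so, but the resulting estimand is not the crossover contrast, and the uncorrected robust error is too small at 30 patients.

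Fourth, the 0.88 threshold depends on assumptions. This also stands. If moderate meant 0.8 SD, a correlation of about 0.66 would suffice. From 0.4 to 0.6 SD the requirement stays above 0.82. The effect of an older baseline scan on r is unknown and concerns only some patients, but it makes a very high correlation harder to presume.

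Finally, PET is not a primary measure, and a trial labelled proof of concept may reasonably include an exploratory imaging subset. That limits the weight of the point without making the power statement correct.

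**Conclusion.** The concern holds. As written, section 11.1 attributes to FDG-PET/CT a power that its design does not have unless the baseline to month-3 correlation is very high: about 0.88 to 0.89 for 0.5 SD at two-sided 5%. At correlations of 0.5 to 0.8, power is 33% to 60%, and unadjusted it is 26%. The effect size, the significance level and every correlation are assumptions, because the plan states none of them. The crossover-specific parts of section 11 cannot be applied to PET. The sentence is not disputed for variables measured in both periods in the full sample, and the primary analysis is unaffected. The plan should be corrected before PET results are interpreted.

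**What to change.** **Section 11.1.** Limit the power sentence to variables scheduled in both periods for the full sample. This also removes the HDL mass-spectrometry work in section 8.1.1, for which "HDL oxidation and proteome profiles will be determined by MS in a subset of patients in the trial" with no size given.

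**Section 11.** Except FDG-PET/CT from the four-occasion description and from the matched-pair, carryover, period and two-baseline components. Specify a comparison of month-3 PET by first-period assignment, adjusted for baseline, for example ANCOVA with t-based inference. If the GEE is kept, name a small-sample correction to the robust standard error for 30 patients.

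State the PET difference detectable with 80% power, with the correlation given as an assumption: about 0.64 SD at r = 0.8, rising to 1.06 SD unadjusted. Commit to reporting the 95% interval, so that a null result is not read as no effect.

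**Cost.** Wording only, including a short analysis specification for PET. No extra patients or scans are needed. The stated power for PET becomes less favourable.
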